- f. Perform tests for Hepatitis B surface antigen (HBsAg), hepatitis B core antibody, hepatitis A virus antibodies (immunoglobulin M), HCV antibody (anti-HCV) confirmed by reflex testing (HCV-RNA) and HIV antigen/antibody (type 1 and/or type 2) at screening.
- g. Perform screening test for amphetamines, barbiturates, benzodiazepines, cannabinoids, cocaine and opiates at screening visit. Repeat urine drug screening before study immunization.
- h. Serum pregnancy test will be done at the screening visit. Urine pregnancy test will be done at study immunization (day 1) and day 30 visits. Not necessary for female subjects who are not of childbearing potential (e.g., post-menopausal [defined as at least 1 year without any menses] or documented surgically sterile) at screening and dosing visit.
- i. Body temperature, blood pressure and pulse rate will be assessed in a sitting position. At the dosing visit, body temperature, blood pressure, pulse rate and respiratory rate will be assessed predose and approximately 30 min and 1 hour postdose. Predose vital signs should be collected close to the vaccination and should not be more than 30 minutes prior to the dose administration. Body temperature will be collected by the subject daily through day 7 following the study immunization.
- j. Perform test for hematology (hemoglobin, hematocrit, erythrocytes, leukocytes, differential WBC, platelets), biochemistry (sodium, potassium, calcium, chloride, glucose, total cholesterol, triglycerides, blood urea nitrogen, creatinine, total protein, albumin, c-reactive protein), coagulation profile (prothrombin time, activated partial thromboplastin time, fibrinogen), hepatic profile (alkaline phosphatase, aspartate transaminase, alanine transaminase, γ-glutamyltransferase, total bilirubin, lactate dehydrogenase), urinalysis (using dipstick protein, glucose, pH, blood, leukocytes, urobilinogen, bilirubin, ketones, nitrite, urine microscopy [optional]).
- k. CCI
- 1. Sample collection to test for serum anti-biotin antibodies should be repeated at the day 180 visit if tested positive on day 30. Biotin levels will be measured in the same sample if the sample is positive for anti-biotin.
- Please see Laboratory Manual for more details.
- n. All concomitant medications or therapies administered from the time the informed consent form (ICF) is signed through day 30 follow up visit will be collected. *Footnotes continued on next page*

o. Subject must remain at site for the first 60 minutes following the injection. Local reactogenicity will be evaluated at 1 hour by site staff and entered into an electronic diary by the subject while on site. The subject will evaluate local and systemic reactogenicity symptoms except for joint pain/arthralgia as per Appendix 12.7 daily and record the results in the electronic diary daily through day 7 following study immunization. On day 7, subject will be questioned if he/she experienced any joint pain/arthralgia or other illness, which is not incorporated into the reactogenicity assessment, in the electronic diary.

p. All observed or spontaneously reported AEs, inclusive of MAAEs, PIMMCs and NOCDs will be documented,. AEs will be assessed at the study immunization visit, before and approximately 60 minutes after immunization. MAAEs will be reported through day 180. The investigator will avoid leading questions to influence reporting of AEs.

Table 2 Schedule of Assessments - Stage 2: Subjects 65 to 85 Years of Age, PCV13 Naïve (Group 2)

Assessments	Screeninga	Dosing 2	Follow-up		
Visit Number	1		3	4	5
Visit Day (Window)	-40 to -3	1	7 (+1)	30 (±2)*	180 (±14)§
Informed Consent ^b	X				
Inclusion/Exclusion Criteria	X	X†			
Randomization ^c		Χţ			
Demographics	X				
Medical History ^d	X	Χţ			
Physical Examination ^e	X	Χţ		X	
Routine 12-lead ECG	X	Χţ	X	X	
Virology ^f	X				
Height, Body Weight	X				
Study Immunization		X			
Vital Signs (blood pressure, pulse rate, body temperature) ^g	X	Χţ	X	X	
Clinical Laboratory Tests (hematology, biochemistry, coagulation profile, hepatic profile, urinalysis) ^h	X	X†‡	X	X	
CCI					
Serum sample for Immunogenicity ^j		X†		X	
Serum sample for Anti-biotin Antibodies		Χ†		X	X^k
Whole-blood sample for T-cell Immune Response Measurement		Χ†	X	X	
Prior/Concomitant Medication ¹					
Reactogenicity ^m			\rightarrow		
AEs ⁿ				\rightarrow	
SAEs ⁿ					
MAAEs including PIMMCs and NOCDs ⁿ					

Footnotes appear on next page

- CONFIDENTIAL -

AE: adverse event; ECG: electrocardiogram; MAAE: medically attended adverse event; NOCD: new-onset chronic disease; PCV13: Prevnar 13; PIMMC: potential immune-mediated medical conditions; SAE: serious adverse event; WBC: white blood cell.

- † To be performed prior to administration of study vaccine. **Note:** Vital signs will also be performed after the administration of the study vaccine.
- ‡ Not required if collected at a screening visit, which is \leq 7days from dosing visit.
- § Visit conducted as a phone call unless anti-biotin antibodies were elevated at day 30 visit.
- * If a subject has received any systemically absorbed antibiotics between day 1 and day 30, the visit should take place at least 7 days after the last dose of the antibiotics.
- a. Screening will be completed up to 40 days prior to study immunization. Subjects will be assigned a subject number for use throughout the study at the screening visit via the Interactive Response Technology (IRT) system.
- b. Informed consent must be obtained prior to the performance of any study-related procedure and before randomization.
- c. Subjects will be randomized via the IRT system at the dosing visit.
- d. Medical history will be collected at screening in order to assess Inclusion/Exclusion criteria and will be reconfirmed prior to study immunization.
- e. A physical examination will be performed at the screening visit (days -40 thru -3), prior to study immunization (day 1) and day 30 visits.
- f. Perform tests for Hepatitis B surface antigen (HBsAg), hepatitis A virus antibodies (immunoglobulin M), HCV antibody (anti-HCV) confirmed by reflex testing (HCV-RNA) and HIV antigen/antibody (type 1 and/or type 2) at screening.
- g. Body temperature, blood pressure and pulse rate will be assessed in a sitting position. At the dosing visit, body temperature, blood pressure, pulse rate and respiratory rate will assessed predose at approximately 30 min and 1 hour postdose. Predose vitals should be collected close to the immunization and should not be more than 30 minutes prior to the dose administration. Body temperature will be collected by the subject daily through day 7 following the study immunization.
- h. Perform test for hematology (hemoglobin, hematocrit, erythrocytes, leukocytes, differential WBC, platelets), biochemistry (sodium, potassium, calcium, chloride, glucose, total cholesterol, triglycerides, blood urea nitrogen, creatinine, total protein, albumin, c-reactive protein), coagulation profile (prothrombin time, activated partial thromboplastin time, fibringen), hepatic profile (alkaline phosphatase, aspartate transaminase, alanine transaminase, y-glutamyltransferase, total bilirubin, lactate dehydrogenase), urinalysis (using dipstick - protein, glucose, pH, blood, leukocytes, urobilinogen, bilirubin, ketones, nitrite, urine microscopy [optional]).
- Immunogenicity data will be provided to the investigative site when available to support decision-making for the standard of care.
- k. Sample collection to test for serum anti-biotin antibodies should be repeated at the day 180 visit if tested positive on day 30. Biotin levels will be measured in the same sample if the sample is positive for anti-biotin.
- 1. All concomitant medications or therapies administered from the time the informed consent form (ICF) is signed through day 30 follow-up visit will be collected.
- m. Subject must be under direct supervision for the first 60 minutes following the injection. Local reactogenicity will be evaluated at 1 hour by site staff and entered into the electronic diary by the subject while on site. The subject will evaluate local and systemic reactogenicity symptoms except for joint pain/arthralgia as per Appendix 12.7 daily and record the results on an electronic diary daily through day 7 following the study immunization. On day 7, subject will be questioned if he/she experienced any other illness, which is not incorporated into the reactogenicity assessment, in the electronic diary.
- n. All observed or spontaneously reported AEs, inclusive of MAAEs, PIMMCs and NOCDs will be documented. AEs will be assessed at the study immunization visit, before and approximately 60 minutes after immunization. MAAEs will be reported through day 180. The investigator will avoid leading questions to influence reporting of AEs.

02 Dec 2019 Astellas Page 33 of 111

Table 3 Schedule of Assessments - Stage 2: Subjects 65 to 85 Years of Age and Received PCV13 Within a Year of Randomization (Group 3)

Assessments	Screeninga	Dosing	Follow-up
Visit Number	1	2	3
Visit Day (Window)	-40 to -3	1	30 (±2)
Informed Consent ^b	X		
Inclusion/Exclusion Criteria	X	Χţ	
Vaccine assignment ^c		Χţ	
Demographics	X		
Medical History ^d	X	Χţ	
Physical Examination ^e	X	Χţ	X
Routine 12-lead ECG	X	Χţ	X
Virology ^f	X		
Height, Body Weight	X		
Study Immunization		X	
Vital Signs (blood pressure, pulse rate, body temperature) ^g	X	Χţ	X
Clinical Laboratory Tests (hematology, biochemistry, coagulation profile, hepatic profile, urinalysis) ^h	X	X†‡	X
CCI			
Serum sample for Immunogenicity		Χţ	X
Prior/Concomitant Medication ^j			\rightarrow
AEs^k	<		
SAEs ^k			\rightarrow
MAAEs including PIMMCs and NOCDs ^k			\rightarrow

AE: adverse event; ECG: electrocardiogram; MAAE: medically attended adverse event; NOCD: new-onset chronic disease; PCV13: Prevnar 13; PIMMC: potential immune-mediated medical conditions; SAE: serious adverse event; WBC: white blood cell.

Footnotes continued on next page

[†] To be performed prior to administration of study vaccine. **Note:** Vital signs will also be performed after the administration of the study vaccine.

[‡] Not required if collected at a screening visit, which is \leq 7days from dosing visit.

- CONFIDENTIAL -

a. Screening will be completed up to 40 days prior to study immunization. Subjects will be assigned a subject number for use throughout the study at the screening visit via the Interactive Response Technology (IRT) system.

- b. Informed consent must be obtained prior to the performance of any study-related procedure and before assigning vaccine via the IRT system.
- c. Subjects will be assigned a vaccine via the IRT system at the dosing visit.
- d. Medical history will be collected at screening in order to assess Inclusion/Exclusion criteria and will be reconfirmed prior to study immunization.
- e. A physical examination will be performed at screening visit, prior to study immunization (day 1) and day 30 visits.
- f. Perform tests for Hepatitis B surface antigen (HBsAg), hepatitis A virus antibodies (immunoglobulin M), HCV antibody (anti-HCV) and HIV antigen/antibody (type 1 and/or type 2) at screening.
- g. Body temperature, blood pressure and pulse rate will be assessed in a sitting position.
- h. Perform test for hematology (hemoglobin, hematocrit, erythrocytes, leukocytes, differential WBC, platelets), biochemistry (sodium, potassium, calcium, chloride, glucose, total cholesterol, triglycerides, blood urea nitrogen, creatinine, total protein, albumin, c-reactive protein), coagulation profile (prothrombin time, activated partial thromboplastin time, fibrinogen), hepatic profile (alkaline phosphatase, aspartate transaminase, γ-glutamyltransferase, total bilirubin, lactate dehydrogenase), urinalysis (using dipstick - protein, glucose, pH, blood, leukocytes, urobilinogen, bilirubin, ketones, nitrite, urine microscopy [optional]).
- All concomitant medications or therapies administered from the time the informed consent form (ICF) is signed through day 30 follow-up visit will be collected.
- k. All observed or spontaneously reported AEs, inclusive of MAAEs, PIMMCs and NOCDs will be documented. AEs will be assessed at the study immunization visit, before immunization and through day 30. The investigator will avoid leading questions to influence reporting of AEs.

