2.3 Endpoints

Stage 1:

Primary Endpoints

Safety and tolerability of ASP3772 will be assessed by:

- Treatment-emergent adverse events (TEAEs) including MAAEs, PIMMCs and NOCDs
- Vital signs (body temperature, blood pressure and pulse rate)
- Reactogenicity assessed using solicited adverse reactions recorded daily by the subject through day 7 postimmunization. These include local and systemic reactions with a predefined grading scale. Local reactions are pain, tenderness, redness/erythema and swelling/induration. Systemic reactions are nausea/vomiting, diarrhea, headache, fever, fatigue, and muscle discomfort or pain/myalgia. Joint pain/arthralgia through day 7 postimmunization will be assessed once by subject recall at the day 7 visit.

Additional safety assessments include laboratory values, ECGs and physical examinations.

Secondary Endpoints

Endpoints used to assess the immunological response on day 30 for the 13 serotypes contained in PCV13:

- Functional OPA activity for each serotype characterized by an OPA titer⁻¹ response expressed as the reciprocal of the serum dilution that causes a 50% reduction in the colony-forming units
- Pneumococcal serotype-specific anticapsular PS IgG for each serotype

Endpoints used to assess the immunological response on day 30 for the 11 serotypes unique to ASP3772:

- Geometric mean fold rise (GMFR) in anticapsular PS IgG at 30 days relative to pre-immunization
- Proportion of subjects with $a \ge 4$ -fold increase in anticapsular PS IgG
- Functional OPA activity expressed as an OPA titer-1

02 Dec 2019 Astellas Page 44 of 111

Stage 2 Group 2:

Primary Endpoints

Safety and tolerability of ASP3772 will be assessed by:

- TEAEs including MAAEs, PIMMCs, and NOCDs
- Vital signs (body temperature, blood pressure and pulse rate)
- Reactogenicity assessed using solicited adverse reactions recorded daily by the subject through day 7 postimmunization. These include local and systemic reactions with a predefined grading scale. Local reactions are pain, tenderness, redness/erythema and swelling/induration. Systemic reactions are nausea/vomiting, diarrhea, headache, fever, fatigue, joint pain/arthralgia and muscle discomfort or pain/myalgia.

Additional safety assessments include laboratory values, ECGs and physical examinations.

Secondary Endpoints

Endpoints used to assess the immunological response on day 30:

- Functional OPA activity for each serotype characterized by an OPA titer⁻¹ response

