5.4.3 Reactogenicity

Subjects will remain at the study site 60 minutes after the injection for safety evaluation. Subjects may be discharged after 60 minutes at the discretion of the investigator. Local and systemic reactogenicity will also be reported for each of 7 consecutive days following the study injection.

Reactogenicity will be assessed using solicited adverse reactions from the time of immunization (day 1) up to 7 days postimmunization. These include local and systemic reactions with a protocol-specified predefined grading scale (see [Appendix 12.6 Grading of Local Reactogenicity; Appendix 12.7 Grading of Signs of Systemic Reactogenicity; and Appendix 12.8 Grading of Laboratory Abnormalities]). Local reactions are pain, tenderness, redness/erythema and swelling/induration. Systemic reactions are nausea/vomiting, diarrhea, headache, fever, fatigue, joint pain or arthralgia and muscle discomfort or pain/myalgia. The daily maximum measurement of local and systemic reactogenicity signs will be recorded by the subject during the 7-day period using an electronic subject electronic diary. For Stage 1, subjects will be questioned at the day 7 visit if they experienced any joint pain/arthralgia through their day 7 visit postimmunization. If their response is yes, they will be asked to provide the degree of severity using a 4-category grading scale from 1 (no interference with activity) to 4 (ER visit or hospitalization) as per Appendix 12.7. For Stage 2, assessments of joint pain/arthralgia will be collected daily through day 7 using the electronic diary. All subjects will be questioned if they experienced any other illness through day 7 postimmunization on their day 7 visit. Reactogenicity reactions will be reported as Clinical Events. If the reactogenicity reaction extends beyond 7-day period or if serious, it will be recorded as an AE, and followed until resolution or deemed medically stable. Subjects will be instructed to contact the site during the 7 consecutive days following an injection to report any reaction \geq grade 2. All local and systemic reactions \geq grade 3 require confirmation by a health care professional.

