Fatigue	No interference with activity	Some interference with activity	Significant; prevents daily activity	ER visit or hospitalization
Arthralgia*	No interference with activity	Some interference with activity	Significant; prevents daily activity	ER visit or hospitalization
Myalgia	No interference with activity	Some interference with activity	Significant; prevents daily activity	ER visit or hospitalization
Illness or clinical AE (as defined according to applicable regulations) †	No interference with activity	Some interference with activity not requiring medical intervention	Prevents daily activity and requires medical intervention	ER visit or hospitalization

AE: adverse event; ER: emergency room; IV: intravenous.

Reference

Guidance for Industry titled "Toxicity Grading Scale for Healthy Adult and Adolescent Volunteers Enrolled in Preventive Vaccine Clinical Trials" issued by US Department of Health and Human Services Food and Drug Administration Center for Biologics Evaluation and Research on September 2007.

02 Dec 2019 Astellas Page 91 of 111

^{*} Stage 1, subjects will be questioned on day 7 visit if they experienced any joint pain/arthralgia through day 7 and if yes, the site personnel will report it as a clinical event using this grading scale. Stage 2 subjects will report arthralgia daily on electronic diary through day 7 postimmunization.

[†] Subjects will be questioned on day 7 if they experienced any other illness through day 7 postimmunization and if yes, the site personal will report it as a clinical event using this grading scale.

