- g. Body temperature, blood pressure and pulse rate will be assessed in a sitting position. At the dosing visit, body temperature, blood pressure, pulse rate and respiratory rate will be assessed predose at approximately 30 min and 1 hour postdose. Predose vitals should be collected close to the immunization and should not be more than 30 minutes prior to the dose administration. Body temperature will be collected by the subject daily through day 7 following the study immunization.
- h. Perform test for hematology (hemoglobin, hematocrit, erythrocytes, leukocytes, differential WBC, platelets), biochemistry (sodium, potassium, calcium, chloride, glucose, total cholesterol, triglycerides, blood urea nitrogen, creatinine, total protein, albumin, c-reactive protein), coagulation profile (prothrombin time, activated partial thromboplastin time, fibrinogen), hepatic profile (alkaline phosphatase, aspartate transaminase, alanine transaminase, γ-glutamyltransferase, total bilirubin, lactate dehydrogenase), urinalysis (using dipstick - protein, glucose, pH, blood, leukocytes, urobilinogen, bilirubin, ketones, nitrite, urine microscopy [optional]).
- i. CCI [REDACTED]
- j. Immunogenicity data will be provided to the investigative site when available to support decision-making for the standard of care.
- k. Sample collection to test for serum anti-biotin antibodies should be repeated at the day 180 visit if tested positive on day 30. Biotin levels will be measured in the same sample if the sample is positive for anti-biotin.
- l. All concomitant medications or therapies administered from the time the informed consent form (ICF) is signed through day 30 follow-up visit will be collected.
- m. Subject must be under direct supervision for the first 60 minutes following the injection. Local reactogenicity will be evaluated at 1 hour by site staff and entered into the electronic diary by the subject while on site. The subject will evaluate local and systemic reactogenicity symptoms except for joint pain/arthralgia as per Appendix B daily and record the results on an electronic diary daily through day 7 following the study immunization. On day 7, subject will be questioned if he/she experienced any other illness, which is not incorporated into the reactogenicity assessment, in the electronic diary.

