7.5.2 Clinical Events

Clinical events capturing reactogenicity will be collected by the subject in the electronic daily diary. Specific local reactions requiring responses are pain, tenderness, redness/erythema, swelling, hardness, and induration at the immunization site. Systemic reactions are nausea, vomiting, diarrhea, headache, fever, tiredness (fatigue), myalgia/muscle pain, and arthralgia with grades 1-4 defined for each. Subjects in stage 1 will be asked to report joint pain/arthralgia through day 7 postimmunization during the day 7 visit. This addition was requested by the FDA after the electronic diary was being used at the sites. The ePRO device will be revised for Stage 2 so that subjects will be asked to report symptoms of arthralgia daily for 7 days post immunization. Additionally, elevated daily body temperature will be summarized by grade: grade 1 mild (100.4-101.1), grade 2 moderate (101.2 – 102.0), grade 3 severe (102.1 – 104) grade 4 potentially life threatening (>104).

Data will be summarized for each study day collected in the diary (day 1 thru day 7) by grade and overall. The number of subjects and percentage who experience each type of reaction will

be provided. The maximum grade for each type of reaction (number and percentage of subjects) will be provided.

At the Day 7 visit the investigator will assess each type of reactogenicity and based on the discussion with the subject will assess these as related or not. Those that are assessed as not related by the investigator will be excluded from a second table summarizing related reactogenicity events. The maximum grade for each type of related reaction (number and percentage of subjects) will be provided. In the event there are none judged as not related, this summary will not be produced.

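### Footnote m of Table 2 excludes joint pain/arthralgia from the Group 2 daily diary, against the Stage 2 primary endpoint and the text of both documents

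*Protocol*

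**What the plan says.** The schedule excludes the item. Protocol Table 2 footnote m, for Group 2, reads "The subject will evaluate local and systemic reactogenicity symptoms except for joint pain/arthralgia as per Appendix 12.7 daily". The SAP reproduces the table, and its footnote m reads "The subject will evaluate local and systemic reactogenicity symptoms except for joint pain/arthralgia as per Appendix B daily". The Day 7 question in the protocol footnote is "On day 7, subject will be questioned if he/she experienced any other illness, which is not incorporated into the reactogenicity assessment".

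The rest of the plan includes the item:

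- Protocol 2.3, Stage 2 Group 2 primary endpoints, lists the solicited reactions that the subject records daily through day 7: "Systemic reactions are nausea/vomiting, diarrhea, headache, fever, fatigue, joint pain/arthralgia and muscle discomfort or pain/myalgia". The synopsis has the same list.
- Protocol 5.4.3: "For Stage 2, assessments of joint pain/arthralgia will be collected daily through day 7 using the electronic diary".
- Protocol Appendix 12.7, note to the arthralgia row: "Stage 2 subjects will report arthralgia daily on electronic diary through day 7 postimmunization".
- SAP 7.5.2: "The ePRO device will be revised for Stage 2 so that subjects will be asked to report symptoms of arthralgia daily". SAP Appendix C carries the same Stage 2 note as protocol Appendix 12.7. SAP 6.2.1.6 describes the same device revision, although it words the item as arthritis.

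For Stage 1, footnote o of Table 1 has the same diary exclusion, but its Day 7 question names the item: "On day 7, subject will be questioned if he/she experienced any joint pain/arthralgia or other illness".

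**The concern.** The footnote is an operative instruction about what the subject records, and it excludes a named component of a primary endpoint. Four parts of the plan depend on the data:

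- **Reporting and comparison.** SAP 7.5.1 summarises arthralgia by grade. It compares the severity of each reaction type, and the number of systemic reactions per subject, between each ASP3772 dose and PCV13. Without arthralgia, one severity comparison disappears and the count of systemic reactions is one item short.
- **Daily profile.** SAP 7.5.2 tabulates reactions by diary day and by maximum grade. Both need daily records.
- **No repair afterwards.** Protocol 8.1 allows no additional diary data after the daily 24-hour window and treats uncollected entries as missing. Protocol 7.10 imputes no missing data of this kind.
- **Safety review.** Reactogenicity of grade 3 or higher enters the escalation criteria (protocol 5.1.2) and the cohort stopping rules (protocol 5.1.5). A reaction that is not solicited is less likely to be counted there.

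The SAP adds that joint pain reporting was requested by the FDA after the Stage 1 diary was already in use, which is why the device was to be revised for Stage 2.

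**Working it through.** No sample-size, power or error-rate figure bears on this point. The check is a comparison of texts, followed by a count of scope.

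**1. Is the item in or out of the Stage 2 diary?**

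| Place | Stage 2 arthralgia in the daily diary? |
|---|---|
| Protocol Table 2, footnote m | Excluded |
| SAP Table 2, footnote m | Excluded |
| Protocol synopsis and 2.3 (primary endpoint) | Included |
| Protocol 5.4.3 | Included |
| Protocol Appendix 12.7 | Included |
| SAP 6.2.1.6 | Included (worded as arthritis) |
| SAP 7.5.2 | Included |
| SAP Appendix C | Included |

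The protocol footnote also contradicts its own reference: it cites Appendix 12.7, which says that Stage 2 subjects report arthralgia daily.

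**2. Is the footnote current text?** Yes. The summary of changes for Amendment 2 shows edits to the Table 2 screening window and to footnotes a, e, f and g. Footnote m is not among them. The SAP already carries the 40-day Stage 2 screening period and still has the exclusion.

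**3. How did it probably arise?** In Stage 1 the diary lacked the item, so footnote o pairs the diary exclusion with a Day 7 recall question. Footnote m has lost the recall question but kept the exclusion. That fits a partial update, in which the recall question was removed because the diary took over and the exclusion was left behind. This is an inference from the two footnotes; the documents do not state it.

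**4. What would be captured if footnote m were followed literally?**

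- Daily diary: no arthralgia.
- Day 7 question: other illness only, and limited to illness outside the reactogenicity assessment. Under 5.4.3 and Appendix 12.7 arthralgia belongs to that assessment, so a subject or site might not report it here. A positive answer would be graded once, on the Appendix 12.7 scale.
- Spontaneous adverse event report (footnote n): possible, but unsolicited.

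So some capture remains. What would be lost is the solicited, daily-graded record that the endpoint calls for.

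**5. Scope of the exposure.** Inputs: cohort sizes from protocol 2.2.1, the reaction list from protocol 2.3, and diary days 1 to 7 from SAP 7.5.2.

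- Subjects under Table 2: 3 × 132 = 396, of whom 3 × 99 = 297 receive ASP3772 and 3 × 33 = 99 receive PCV13.
- Reactions affected: 1 of 7 (nausea/vomiting, diarrhea, headache, fever, fatigue, joint pain/arthralgia, myalgia).
- Daily arthralgia entries planned: 396 × 7 = 2,772.

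These figures are the ceiling if the footnote overrode every other section. They do not forecast loss.

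**6. Appendix reference in the SAP.** SAP footnote m sends the reader to Appendix B for both local and systemic symptoms. Appendix B grades local reactions only. Systemic reactions, including arthralgia, are graded in Appendix C.

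**The case against.** The strongest reply is that the intended design is clear and that one leftover phrase will not change what is collected. Diary items are set by the device, and SAP 6.2.1.6 and 7.5.2 both say that the device will be revised for Stage 2 to ask daily. Section 5.4.3 and Appendix 12.7 state the Stage 2 rule explicitly, and a site that follows the footnote's own reference reaches that rule. Nothing outside the footnote suggests that the prompt would be absent, and nothing in the documents says that sites work from the schedule in preference to the body text. All of this stands. It makes actual loss unlikely and limits the weight of the point. It does not remove the contradiction, which sits in a collection instruction in both documents.

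Three stronger readings are tempting and are not supported:

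- **Arthralgia is collected nowhere in Stage 2.** A reader of Table 2 alone might infer this. It ignores the question on other illness, spontaneous adverse event reporting and the stated device revision.
- **The missing Day 7 joint-pain question is a second defect.** Under 5.4.3 and Appendix 12.7 that question belongs to Stage 1 only, where the diary lacked the item. Its absence from footnote m is consistent with moving arthralgia into the Stage 2 diary.
- **The plan chose to omit arthralgia in Stage 2.** The primary endpoint and the body text of both documents show the opposite.

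**Conclusion.** The point holds as an internal inconsistency that is wrong as written and should be corrected. Footnote m of Table 2, in the protocol and in the SAP, contradicts the Stage 2 primary endpoint and the collection rules in both documents.

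Its size is conditional. If the footnote were followed, 1 of 7 systemic reactions would lack solicited daily grading in about 396 Group 2 subjects. If the Stage 2 device is revised as the SAP states, little or nothing is likely to be lost. The documents do not show the final diary content, so they cannot settle which case applies. The conclusion rests on the current wording of the two footnotes and assumes nothing about how sites behaved.

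**What to change.** 1. In footnote m of Table 2, in both the protocol and the SAP, delete the words that except joint pain/arthralgia from the daily evaluation. The footnote then agrees with protocol 2.3, 5.4.3 and Appendix 12.7, and with SAP 6.2.1.6, 7.5.2 and Appendix C.
2. In SAP footnote m, change the reference from Appendix B alone to Appendices B and C, so that local and systemic grading are both covered.
3. Leave the Day 7 question as it is. No joint-pain recall question is needed in Stage 2 once the diary carries the item.

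The cost is a wording change to one footnote in each document. It adds no procedure, visit or analysis. It would be sensible to confirm at the same time that the Stage 2 diary build contains the daily arthralgia item, since that decides whether the inconsistency has any effect on the data.
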